9.6. Undertaking Supplemental “As Treated” Analyses

The primary analysis for the PROVEN trial is an “intention to treat” analysis in which the outcomes of target group long-stay nursing home residents of intervention facilities are compared to those of identically defined residents of control facilities. This approach assumes that most eligible subjects in the intervention facilities will be directly exposed to the intervention by watching one of the videos. While there may be an indirect effect on the facility culture related to the availability of the videos and increased discussions of “comfort care”, direct exposure by watching the video is assumed to be the more powerful and complete approach to delivering the intervention.

As part of the PROVEN trial, intervention staff are to record when patients are offered and subsequently shown a video at each facility. The total number of long-stay target residents who “should have been shown” the video and the total number of such patients who actually viewed the video at the facility are routinely calculated. Although some families and patients may have watched videos online, we are unable to identify this number precisely. Thus, the proportion of patients whom staff report as having watched the video is a reasonable proxy for the level of implementation of the intervention across intervention facilities. As of the end of February 2018, only 12.5% of the long stay residents in System 1 facilities and 31.4% in System 2 facilities were

reported as having been shown a video. However, there is substantial variation in the rates of target residents reported as having been shown the video, ranging from 0% to over 80%. This raises the question of whether it would be possible to compare the outcomes of patients exposed to the video who reside in nursing centers that embraced the video-assisted advance care planning intervention to similar control patients from similar facilities.

The principal stratification framework¹³⁸ has been proposed as a possible solution to address non-compliance in randomized trials and is appropriate in this instance because facilities can be classified on the basis of the extent to which they implemented the intervention. The basic principal stratification framework initially posits that patient i has two possible potential compliances: compliance under the intervention arm, $D_i(1)$, and compliance under the control arm $D_i(0)$. Using these potential states (outcomes), we can classify patients into different strata and calculate the average effect within each stratum. When patients can either comply with the intervention or not, there are four principal strata: compliers ($D_i(1) = 1, D_i(0)=0$); never takers ($D_i(1) = 0, D_i(0)=0$); always-takers ($D_i(1) = 1, D_i(0)=1$); and defiers ($D_i(1) = 0, D_i(0)=1$). For each patient, only one of these compliance outcomes is observed.

Studies, such as ours, in which patients in the control group cannot obtain the intervention are commonly referred to as one-sided non-compliance. There are three possible strata: (1) assigned to the intervention and did not take it – never-takers; (2) assigned to the intervention and receive it – compliers; (3) assigned to the control and received control – can be either never-takers or compliers. Thus, a statistical methodology that is aimed at identifying the effect among compliers needs to identify among the control group those that would have not refused the treatment were it to have been offered. Numerous studies have fruitfully employed the principal stratification framework to estimate the effects of an intervention on compliers.^{139, 140, 141, 142}

We will estimate the effect of the intervention on the compliers who reside in facilities that have adopted the video-assisted intervention by creating a hierarchy including compliance at the facility level and, within facility, adjusting for compliance status at the individual level. As noted, we find high variability between intervention facilities related to the likelihood that a patient would receive the intervention. Because the intervention is delivered almost entirely through the mechanism of facility staff, we assume that individual compliance is affected by the facility's and patient's characteristics. We can classify the treated facilities into compliance groups based on the reported show rates and/or based upon more qualitative assessment of research staff working to implement the intervention with participating facilities. Compliance groups can be constructed and facility-level characteristics that are predictive of the compliance status can be identified using the large amount of facility and aggregated resident data we have available. Preliminary analyses reveal that several facility-level characteristics are correlated with the video offer and show rates. We propose developing a Bayesian model to multiply impute the compliance groups of control facilities based upon these types of facility-level characteristics for which we have considerable data elements. The net result is a pool of high intervention implementers and a corresponding set of control facilities with similar predicted compliance.

Preliminary data suggest that facility-level characteristics are more correlated with facility offer rates than to facility show rates. This suggests that, although facility characteristics influence the offer rate, patient-level characteristics are also important determinants of actually watching the video. Thus, we will develop a modeling framework that identifies the compliance status for each patient within the hierarchy of the cluster randomized trial. This approach will first impute compliance status group for control facilities and then will impute patient-level

compliance status within each facility compliance group. This two-part imputation is performed using Bayesian models to predict compliance status for each facility, followed by a Bayesian model of patient-level compliance within facilities with similar predicted compliance status. Formally, let $Y_i(W)$ represent the potential outcomes for patient i under the intervention, $W=1$, or the control, $W=0$. In addition, let $L_j(1)$ be the average compliance of facility j if it would have been assigned to the intervention arm, and $M_i(1)$ be the compliance of patient i if s/he would have resided in a facility exposed to the intervention. We would estimate the following models:

1. $f(Y_i(1), Y_i(0) | L_j(1), M_i(1), X_i, W_i, Z_j)$ - The potential outcomes conditional on patient's and facility's compliance status, and patient- and facility-level covariates. These models would be hierarchical zero inflated Poisson models.
2. $f(M_i(1) | L_j(1), X_i, W_i, Z_j)$ - The compliances status of patients conditional on the compliance status of the associated facility and on patient- and facility-level covariates. This model would be a hierarchical logistic regression model.
3. $f(L_j(1) | Z_j, W_j)$ - Models the compliances status of facilities conditional on facility characteristics. This model would be a linear regression model (with possible transformation) where X are patient level characteristics and Z are facility level characteristics.

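### Section 9.6 groups intervention homes by actual implementation and control homes by predicted implementation, so an unmeasured home factor could bias the supplemental complier estimate, and no planned analysis would show by how much

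*Combined protocol and SAP*

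**What the plan says.** Section 9.6 adds a principal-stratification analysis to the intention-to-treat comparison, prompted by low and very uneven use of the videos: 12.5% and 31.4% of long-stay residents in the two systems, with home-level rates from 0% to over 80%.

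- Intervention homes: "We can classify the treated facilities into compliance groups based on the reported show rates and/or based upon more qualitative assessment of research staff".
- Control homes: "We propose developing a Bayesian model to multiply impute the compliance groups of control facilities based upon these types of facility-level characteristics".
- Outcome of the grouping: "The net result is a pool of high intervention implementers and a corresponding set of control facilities with similar predicted compliance".
- Effect promised: "We will estimate the effect of the intervention on the compliers who reside in facilities that have adopted the video-assisted intervention".
- Facility compliance model (third model in the list): average compliance given facility characteristics Z and arm. "This model would be a linear regression model (with possible transformation) where X are patient level characteristics and Z are facility level characteristics".
- Predictive strength: not quantified, but "facility-level characteristics are more correlated with facility offer rates than to facility show rates".

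The general description of the framework adds that "we can classify patients into different strata and calculate the average effect within each stratum". The section states no assumption about home factors outside Z and no sensitivity analysis for them.

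**The concern.** The two sides of the comparison are selected differently. A high-implementing intervention home carries everything that made it one, measured or not. Its control counterpart carries only the part that Z predicts. Leadership or a palliative culture, so far as Z misses it, could raise show rates and lower transfers at once, and would then look like a video effect.

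The documents make such a factor plausible. Section 9.5 reports that transfer rates differ between homes after adjustment for patient risk. Section 9.6 says that delivery runs almost wholly through facility staff, and its staff judgement of implementation exists only in the intervention arm.

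The stake is how the supplemental result is read. With show rates this low, a null primary result is possible, and a favourable complier estimate beside it would be hard to interpret without further output.

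**Working it through.** **Calibrating between-home variation.** Section 9.6 gives no figure, so I took one from Section 9.2: 103 homes per arm for 1.51 versus 1.26 transfers per person-year at 90% power. The Hayes–Bennett formula is

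c = 1 + (z_α/2 + z_β)² × [(r0 + r1)/y + k²(r0² + r1²)] / (r0 − r1)²

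Assumptions: two-sided 0.05 (the level is not stated) and y = 42 person-years per home (42 target patients in Section 9.2, one year each). k is not stated, so I solved for it. With k = 0.374:

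1 + 10.51 × [2.77/42 + 0.1399 × 3.868] / 0.0625 ≈ 103

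The same k comes within one home of every entry in the 1.06 and 1.51 rows (82/64/51/41 and 166/129/103/85, against the stated 81/63/50/41 and 165/129/103/84). It does not fit the 2.12 row, which needs about 0.389. This is calibration, not independent reproduction. Rounding to k = 0.37, the SD of the log home rate is √ln(1 + 0.37²) = 0.358.

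**Bias with no video effect.** Write standardised implementation as L = √R²·Z + √(1 − R²)·e, where e is the part that Z does not predict. Let the log transfer rate have correlation −ρ with e, and call the top share p of homes high implementers. Intervention homes are chosen on L itself, so their mean e is √(1 − R²)·φ(c)/p. Control homes are chosen on L imputed from Z, so their mean e is 0. Hence

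spurious log rate ratio, high implementers = −SD × ρ × √(1 − R²) × φ(c)/p

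spurious log rate ratio, low implementers = +SD × ρ × √(1 − R²) × φ(c)/(1 − p)

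For p = 1/3, c = 0.431, φ(c) = 0.3636 and φ(c)/p = 1.091. Example, R² = 0.1 and ρ = 0.4: −0.358 × 0.4 × 0.949 × 1.091 = −0.148, a 13.8% reduction.

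| R² | ρ | High implementers | Low implementers |
|---|---|---|---|
| 0.1 | 0.3 | −10.5% | +5.7% |
| 0.1 | 0.4 | −13.8% | +7.7% |
| 0.5 | 0.3 | −8.0% | +4.2% |
| 0.5 | 0.4 | −10.5% | +5.7% |
| any | 0 | 0 | 0 |

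The planned effect is 0.25/1.51 = 16.6%.

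**Simulation.** With 119 and 241 homes and no video effect, adjusting the contrast for Z left the bias at 8–14% for ρ = 0.3–0.4, and it was nominally significant in 16–45% of trials. Adjustment for Z cannot remove it, because e is by construction what Z misses. In a separate run that selected control homes on their true (in practice unobservable) L, the difference was about zero (−0.01 to +0.01 per person-year).

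**Which extra outputs would help.**

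- The share-weighted average of the two contrasts is p × (high) + (1 − p) × (low) = 0 on the log scale. That equals the true intention-to-treat effect here, so agreement with intention to treat cannot reveal this bias.
- The low-implementer contrast does move, but weakly. With 79 versus 161 homes its standard error is √[(0.358² + 1/(42 × 1.51)) × (1/79 + 1/161)] = 0.052. The shift of 0.041–0.074 is only 0.8–1.4 standard errors. In simulation it was significant in about 9–26% of trials.

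**The case against.** - **Other strata are not excluded.** A reader might infer that 9.6 will report compliers in adopting homes and nothing else. The text does not say so: it says that effects can be calculated within each stratum, and it speaks of compliance groups in the plural. The complier effect is the only one promised, which is a weaker statement. This stands.
- **The size is assumed.** The documents give no value for ρ, its sign, R² or a cut-off. 9.6 also models facility compliance as a continuous average, so the top third is my choice. This stands; 8–14% is an illustration.
- **Z may be rich.** Section 4.3 allows exclusion of homes with recent leadership turnover or bad surveys, and Section 6.1.4 lists staffing and inspection data. Prior hospitalization rates are held for stratification (Section 4.4.3). If these correlate 0.5–0.8 with the trial-period rate (an assumption), the residual SD falls from 0.358 to 0.358 × √(1 − 0.25) = 0.310 or 0.358 × √(1 − 0.64) = 0.215. At unchanged ρ the bias becomes about 7–12% or 5–9%. But 9.6 does not list Z, so this supports a fix more than it removes the problem.
- **A joint fit could use control outcomes.** The outcome model conditions on compliance, so a joint Bayesian fit could let control outcomes inform the imputed groups. 9.6 does not say that they will. L(1) and Y(0) are never observed in the same home, so that link would rest on model form.
- **The show-rate gap is attributed to patients.** 9.6 explains the weaker correlation with show rates by patient characteristics and adds a patient-level compliance model. That is fair; the gap alone does not prove an unmeasured home factor. The patient model still sits within homes grouped as above.
- **A low-implementer effect need not be bias.** 9.6 allows that "there may be an indirect effect on the facility culture" and says that online viewing cannot be counted precisely. This stands and rules out a pass/fail reading.

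**Conclusion.** The asymmetry is in the text: actual implementation in one arm, predicted in the other, with no stated assumption or sensitivity analysis for what the prediction misses. The complier estimate is therefore open to bias in either direction. The illustrative 8–14% spurious reduction rests on between-home variation back-solved from Section 9.2, R² of 10–50%, a top-third cut-off and ρ of 0.3–0.4. It is zero at ρ = 0, and a reversed sign would mask a real benefit.

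A reader might go further and conclude that 9.6 will produce a false benefit, or that the trial's main conclusion is at risk. The documents support neither. Nothing shows that such a factor exists at this strength, the analysis is labelled supplemental, and the primary intention-to-treat comparison of all randomised homes does not depend on it. This is a worthwhile, inexpensive improvement to a secondary analysis.

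**What to change.** In Section 9.6:

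1. Commit to reporting the same model's effect for low-implementing homes and for never-takers, beside the complier/high-implementer effect and the intention-to-treat estimate. Read a clearly non-zero low-implementer effect as a limit on interpretation, not proof of bias. Set no pass/fail rule, and do not use agreement of the weighted average with intention to treat as a check.
2. Add a sensitivity analysis over the correlation between unmeasured implementation and the transfer rate, in both directions. Show how large it must be to account for the complier effect.
3. Include each home's prior hospitalization rate in Z. Form groups on recorded show rates only, without staff judgement, and set the cut-off before outcomes are seen.

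Cost: SAP wording, extra rows from models already planned, and modest new modelling for the sensitivity parameter. No new data are needed. The supplemental result may look less favourable; the primary analysis does not change.

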10. DATA COLLECTION AND QUALITY ASSURANCE

10.1. Data Collection

All data are derived from existing data sources with exception of the Video Status Report User Defined Assessment. Please see *Section 6* which details these sources.

10.2. Data Confidentiality

Brown University's Center for Gerontology and Health Care Research will receive EMR patient-level data from PruittHealth and Genesis HealthCare. Both NH systems have integrated sophisticated EMR systems in their facilities. Genesis HealthCare uses PointClickCare™,⁹⁸ and PruittHealth uses American Health Tech.⁹⁹ The NH networks already have experience extracting MDS from their EMR systems for purposes of submitting mandatory, regular MDS reports to CMS. To protect patient confidentiality, the two corporations will place their data in a SSH secure server and will provide login information to Brown University. Data transfer to Brown University secure servers will be via SFTP protocol with password protection. Once the files have been uploaded to Brown University's servers they will be stored, unmodified, in a secure file location specific to these uploads. They will then be read into SAS datasets, one per file type. Brown University will then notify the facilities that the data was successfully downloaded and extracted, at which point the facilities will remove the data from their servers. All data files will be accompanied by a manifest detailing the number of distinct persons and records expected in them. Brown University will connect to the corporation servers on a monthly basis. Identifiers such as HICs and SSNs, will be included in order to be able to merge these person-level data to the data received from CMS. Brown University's information systems manager will be in charge of the data transfer, and he will replace the HICs and SSNs fields with a Brown University-generated identification number (throughout our different data sources) to allow linkage of data for analytic purposes.

10.3. Data Management

Brown University's Center for Gerontology and Health Care Research will serve as the Data Management/Statistical Center for the PROVEN trial. The Center will be responsible for: 1. Receiving all data from CMS (Medicare, MDS), ii. Receiving all EMR data from PruittHealth and Genesis HealthCare Study facilities, iii. Linking all data sources, and iv. Creating an analytic file and conducting analyses. Brown University investigators and database management staff already receive national MDS, Medicare, and OSCAR data semi-annually or quarterly under several CMS DUAs. There is a well-established data base management structure to linking these files. The only new activity for PROVEN is integration of the EMR data from facilities with CMS Medicare claims and the MDS. The integration will be easily achieved thanks to the availability of HIC and SSN personal identifiers in both the EMR data from facilities and in the CMS Medicare claims and MDS data.

10.4. Data Use Agreements

The Brown University Center for Gerontology has an extensive history of working with ResDac to obtain DUAs to use CMS MDS and Medicare data for NIH funded projects, which will be obtained for this project. DUAs for the data sharing arrangement between Brown University and the two partner health care systems, Genesis HealthCare and PruittHealth have already been obtained. Our team will ensure all DUAs are compliant with NIH requirements.

10.5. Quality Assurance Metrics

For the primary outcome, hospital transfers, we will have a quality control metric which compares hospital transfers as derived from MDS assessments with hospital transfers obtained from Medicare Part A claims for patients who are in the traditional fee-for-service Medicare program.

11. PARTICIPANT RIGHTS AND CONFIDENTIALITY

11.1. Institutional Review Board (IRB) Review

The PROVEN protocol will be reviewed and approved by the Brown University IRB.

11.2. Informed Consent

There are special informed consent considerations for individual patients in this pragmatic, cluster RCT. The NH is the unit of randomization, the intervention is of relatively low risk, and it will be implemented facility-wide as part of the intervention facilities' standard operating procedures for ACP. In the control arm, usual care for ACP will be in place. In both study arms, all data will be ascertained from existing sources. NH administrators, who either agree or disagree to facility participation in the intervention arm are serving as gatekeepers for the study. Thus, we will seek a waiver of individual informed consent so as set forth by the four criteria found in HHS 45 CFR 46:116.¹³⁷

(1) The research involves no more than minimal risk: See *Section 7.1* for rationale for Minimal Risk Determination

(2) The waiver will not adversely affect the rights and welfare of the subjects: All NHs must engage patients and families in ACP as part of routine clinical practice. There is currently no standardized method by which NHs conduct ACP. The ACP Video Program is intended to

enrich ongoing ACP practices in the intervention NHs. Study randomization is at the level of the NH, not the patient. While the patients in the intervention arm are not informed of the study itself they *are* asked whether or not they want to be shown the video. They are free to decline as they are free to decline any type of ACP discussion. Patients in control NHs will be exposed to usual care. For NH residents in both study arms, we will be using data previously collected for non-research purposes (EMR and CMS data. These data will be obtained and managed in a confidential manner for study purposes (*see Sections 10.2*).

(3) The research could not practicably be carried out without the waiver: It would be impossible to conduct this *pragmatic trial* if it required ascertainment of individual informed consent for several reasons. Doing so would undermine the very intent of the pragmatic trial design: to test whether the videos are effective in a “real-world” application under usual conditions. ACP is part of usual NH care and is simply being augmented in the intervention facilities with the videos. Getting written informed consent is not ‘usual’ for everyday NH care. In that vein, members of the NH staff are offering the videos to the patients in the intervention facilities, not the research team. The ACP videos are being integrated into the NHs’ standard operating procedures and offered to ALL NHs residents as part of the facility’s daily work-flow. It would not be feasible for the NH staff to obtain informed consent from all residents being offered the videos, especially since the videos are being integrated into the standard of care in that NH. With regards to data acquisition, all the data used in the study, with the exception of the Video Status Report User Defined Assessment, are already being collected for non-research purposes in both the intervention and control NHs. If permission to use these data were required by way of informed consent, this would have to be done for ALL residents in all facilities by staff in BOTH the control and intervention NHs. It would be impossible and put undue burden on the NH staff and the residents themselves to collect individual consent for the use of their records. Such an approach would once again undermine the pragmatic intent of the study and also dramatically reduce both NH and patient participation to the extent the study would not be possible.

(4) If appropriate, the subjects will be provided with additional pertinent information after participation: We will provide the NH corporations, PruittHealth and Genesis HealthCare, with copies of the reports and manuscripts that result from this project. They are free to share the information with their NHs, and the NHs will be free to share the information with interested families and patients.

